7.2.2.1. Dose-Limiting Toxicity Determination and Maximum Tolerated Dose Definition

Dose-limiting toxicity is defined as an AE that is at least possibly related to the study drug(s) and that occurs during Cycle 1 (the DLT-evaluation period) and does not improve to the National Cancer Institute's (NCI) Common Terminology Criteria for Adverse Events (CTCAE) v4.0 (CTEP 2009) Grade ≤ 2 (unless stated otherwise), despite medical management, including steroids (if applicable). Toxicity that is clearly and directly related to the primary disease or to another etiology is excluded from this definition. The following are considered DLTs, unless noted otherwise:

- Grade 4 neutropenia lasting ≥ 7 days
- Grade 3 or 4 neutropenia complicated by fever or infection of any duration
- Any Grade 4 thrombocytopenia
- Any Grade 3 thrombocytopenia complicated by hemorrhage
- Any Grade 3 or 4 anemia

- Grade 3 or 4 nonhematologic toxicity, including:
 - any Grade 4 irAE
 - any Grade 3 or 4 colitis
 - any Grade 3 or 4 noninfectious pneumonitis irrespective of duration
 - any Grade 3 irAE, excluding colitis or pneumonitis, that does not downgrade to Grade 2 within 3 days after onset of the event despite optimal medical management including systemic corticosteroids or does not downgrade to Grade ≤ 1 or baseline within 14 days
 - any Grade 3 or 4 non-irAE except as noted for transaminases, bilirubin, lipase, or amylase below
 - any liver transaminase elevation $>8 \times$ institutional ULN or total bilirubin (TB) $>5 \times$ institutional ULN
 - creatine kinase elevation $>8 \times$ ULN
- Any Grade 2 pneumonitis that does not resolve to Grade ≤ 1 within 3 days of the initiation of maximal supportive care

The DLT definition excludes the following conditions:

- Grade 3 fatigue lasting ≤ 7 days
- Grade 3 endocrine disorder (thyroid, pituitary, and/or adrenal insufficiency) that is managed with or without systemic corticosteroid therapy and/or hormone replacement therapy and the patient is asymptomatic
- Grade 3 inflammatory reaction attributed to a local antitumor response (for example, inflammatory reaction at sites of metastatic disease, lymph nodes, etc)
- Concurrent vitiligo or alopecia of any AE grade
- Grade 3 IRR (first occurrence and in the absence of steroid prophylaxis) that resolves within 6 hours with appropriate clinical management
- Grade 3 or 4 neutropenia that is not associated with fever or systemic infection that improves by at least 1 grade within 3 days. Grade 3 or 4 febrile neutropenia will be a DLT regardless of duration or reversibility
- Grade 3 or 4 lymphopenia
- Grade 3 thrombocytopenia that is not associated with clinically significant bleeding that requires medical intervention, and improves by at least 1 grade within 3 days
- Isolated Grade 3 electrolyte abnormalities that are not associated with clinical signs or symptoms and are reversed with appropriate maximal medical intervention within 3 days

- Isolated asymptomatic Grade 3 elevation of amylase or lipase without evidence of end organ damage.
- Asymptomatic Grade 3 CK level ($5-10 \times \text{ULN}$: CTCAE v4.0) that is not associated with elevated serum or urinary myoglobins and no evidence of rhabdomyolysis or myositis.
- Asymptomatic Grade 3 AST induction that is accompanied by Grade ≤ 1 ALT and Grade ≤ 1 TB and no change of ALT or TB from baseline levels.

Adverse events meeting DLT criteria that occur beyond Cycle 1 are defined as dose-limiting equivalent toxicities (DLETs). If a patient is believed to be benefitting from study treatment, patients who experience a DLT may continue to receive study treatment upon agreement of the investigator, sponsor, and collaborator.

For the purpose of this study, the MTD is defined as the highest tested dose that has less than 33% probability of causing a DLT. The MTD will be determined as shown in [Table JSCC.3](#) and [Table JSCC.4](#).

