Comparatively, preclinical and clinical studies on CSF-1R–targeted monoclonal antibodies have shown asymptomatic increases in short-lived enzymes, such as LDH, CK, and AST (Cassier et al. 2015; Zhou et al. 2015). These increases in the levels of serum enzymes can be the result of decreases in Kupffer cells, depletion of which is consistent with the expected pharmacologic effect of CSF-1R pathway inhibition on Kupffer cells (Radi et al. 2011).

In clinical studies of LY3022855 monotherapy, increases in serum amylase and lipase (mostly Grades 1 and 2) were noted in 4 and 9 patients, respectively, who received single-agent LY3022855 (of the total of 64 patients) as of 28 January 2017. These patients were treated with 1.25 mg/kg QW, 1.25 mg/kg Q2W, 100 mg QW, or 150 mg QW of LY3022855. One of these patients who was treated with LY3022855 1.25 mg/kg QW developed mild-to-moderate increases in amylase and lipase levels and was ultimately diagnosed with Grade 3 pancreatitis, determined to be dose-limiting. The patient recovered from pancreatitis following study treatment interruption but was subsequently removed from study due to the event. There were no other cases of pancreatitis reported with administration of a single-agent LY3022855 as of 28 January 2017.

These data suggest that elevations of serum levels of enzymes AST, CK, amylase, and lipase, are not necessarily indicative of end organ damage, thus, supporting modification of the DLT criteria in this protocol to allow flexibility to continue dosing with Grade ≥ 2 elevations of AST, CK, amylase, and lipase in certain situations as described in Section 7.2.2.1.

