7.6. Treatment Compliance

Study treatment will be administered I.V. at the investigational site, under the direction of the investigator. As a result, a patient's compliance with study drug administration is ensured. Patients should attend scheduled clinic visits and must comply with study criteria under their control. Deviation(s) from the prescribed dosage regimen should be recorded on the eCRF.

7.6.1. *Evaluable Patients*

Patients in Part A who receive all doses of study treatment for Cycle 1 (DLT-evaluation period) will be considered evaluable for the assessment of a dose level, provided it can be documented whether the patient did or did not experience a DLT within 28 days of Cycle 1, Day 1.

Conversely, any patient in Part A who is discontinued from the study before completing one cycle of study treatment will be deemed nonevaluable for assessment of a dose level, unless they experience a DLT prior to withdrawal. Nonevaluable patients may be replaced to ensure that enough patients complete one cycle of therapy at each dose level for Part A, unless accrual to that cohort has stopped due to a DLT.

Patients who are not evaluable for PK but who complete one cycle of therapy may be replaced upon consultation with the investigator(s) and the sponsor's CRP/CRS to ensure adequate PK data, unless accrual to that cohort has stopped due to a DLT.

Note that the concept of "evaluable" (and, thus, replacement of patients) does not apply to patients in Part B.

8. Safety, Pharmacokinetic, Pharmacodynamic, and Efficacy Data Collection

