Tumor tissue biopsy		X		For Part A (all cohorts) and Part B (ovarian cancer cohort only): A newly obtained core or excisional biopsy of a tumor should be taken only after study eligibility is confirmed. For the NSCLC cohort in Part B a newly obtained core or excisional biopsy should be obtained if an archived tumor sample following the most recent systemic therapy is not available. Refer to the laboratory manual.
Archived tumor tissue	X			An archived tumor sample following most recent systemic treatment if not restricted by local regulations will be requested from all patients in Part B NSCLC cohort. If such an archived biopsy sample is not available, a new biopsy must be obtained for the patient to be eligible to participate in study. Refer to the laboratory manual.
Whole blood for biomarkers			X	Refer to the laboratory manual.
Pregnancy test (local)			X	Applies only to women of childbearing potential. Urine hCG or serum β-hCG is acceptable.

Abbreviations: AE = adverse event; BP = blood pressure; CA125 = cancer antigen 125; CEA = carcinoembryonic antigen; CT = computed tomography (scan); CTCAE = Common Terminology Criteria for Adverse Events; ECG = electrocardiogram; ECOG = Eastern Cooperative Oncology Group; GI = gastrointestinal; hCG = human chorionic gonadotropin; HIV = human immunodeficiency virus; ICF = informed consent form; LVEF = left ventricular ejection fraction; MRI = magnetic resonance imaging; MUGA = multigated acquisition (scan); PR = pulse rate; QTcF = QT interval corrected for heart rate using Fridericia's Correction Formula; RR = respiration rate; T3 = triiodothyronine; T4 = thyroxine; TSH = thyroid-stimulating hormone; v4.0 = Version 4.0 of CTCAE.

On-Study Treatment and Post-Treatment (Follow-Up) Assessments for Combination Therapy: LY3022855 plus Durvalumab

Note that a maximum of 12 months/26 doses of durvalumab treatment is permitted; last infusion at Week 50.

Screening procedures performed for safety within 72 hours prior to Cycle 1 Day 1 (C1D1) do not need to be repeated on C1D1.

Rows with *italicized* font indicate that there is no planned assessment for the time frame shown on the page.

LY3022855 plus Durvalumab Assessment (central or local laboratory indicated, if applicable)	Cycle 1 (Visit 1)						Comments Except for the Cycle 1, Day 1 visit, allowable windows are ± 3 days, unless otherwise indicated. On dosing days, all assessments to be performed preinfusion, unless stated otherwise.
	1	2	3	8	15	22	

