Coagulation (local)							Refer to Attachment 2. As clinically indicated.
Thyroid function (central)	X						Refer to Attachment 2 . Free T3 and free T4 will be measured only if TSH is abnormal or if there is clinical suspicion of an AE related to the endocrine system.
Pancreas function (central)							Refer to Attachment 2.
Tumor markers (local)							
Pharmacogenetic sample	X						Refer to the laboratory manual. Collect once. Sample can be collected at any time, if not collected on C1D1.

LY3022855 plus Durvalumab Assessment (central or local laboratory indicated, if applicable)	Cycle 1 (Visit 1)						Comments Except for the Cycle 1, Day 1 visit, allowable windows are ± 3 days, unless otherwise indicated. On dosing days, all assessments to be performed preinfusion, unless stated otherwise.
	1	2	3	8	15	22	
Relative day within a 28-day cycle:							
Immunogenicity	X					X	If at any time a patient experiences an IRR, attempt to obtain a blood sample for immunogenicity analysis as close to the onset of the event as possible, at the resolution of the event, and 30 d following the event. A portion of the sample taken for immunogenicity testing may be used for PK analysis.
Myoglobin (local)					X		Refer to Attachment 2 . If serum CK Grade ≥ 2 , test for serum and urine myoglobin.
CTCAE v4.0 grading	X			X	X	X	Throughout study as needed. Refer to Section 8.1.1 for reporting guidelines.
Concomitant medications	X			X	X	X	Throughout study as needed.
LY3022855 administration	Refer to Table JSCC.1 for dose frequency during Part A.						For LY3022855 and durvalumab: Part A doses: Refer to Table JSCC.1 .
Durvalumab administration	X				X		Part B doses and dose frequencies to be determined; refer to Section 7.2.2.2 for information.
Pharmacokinetics							
LY3022855 (predose on dosing days, unless noted otherwise)	X	X 2 h post-EOI C1D1 (± 1 h)	X 24 h post-EOI C1D1 (± 4 h)	X 48 h post-EOI C1D1 (± 4 h)	X	X	X The date and the time of all samples must be clearly and accurately recorded. EOI = end of infusion
Durvalumab (predose on dosing days, unless noted otherwise)	X	X Simultaneously with LY PK sample	X Simultaneously with LY PK sample	X Simultaneously with LY PK sample	X	X	X
Pharmacodynamics and tailoring							
Serum	X	X Simultaneously with LY PK sample	X Simultaneously with LY PK sample	X Simultaneously with LY PK sample	X	X	X Serum storage for correlative studies.
Plasma	X						Plasma storage for correlative studies.

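### Amylase and lipase enter the DLT definition and a hold rule, but no planned Cycle 1 test measures them in either combination

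*Protocol*

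**What the plan says.** Protocol section 7.2.2.1 defines DLTs over Cycle 1. Its list of nonhematologic DLTs includes "any Grade 3 or 4 non-irAE except as noted for transaminases, bilirubin, lipase, or amylase below". Among the exclusions is "Isolated asymptomatic Grade 3 elevation of amylase or lipase without evidence of end organ damage". Adverse events that meet the criteria after Cycle 1 are DLETs. Table JSCC.3 sets the durvalumab-combination MTD from Cycle 1 DLTs, and Part B is treated at that MTD unless the sponsor specifies otherwise. Under section 7.6.1 a Part A patient who received all Cycle 1 doses is evaluable "provided it can be documented whether the patient did or did not experience a DLT within 28 days of Cycle 1, Day 1".

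Attachment 2 places amylase and lipase in the central Pancreas Function panel only; neither the local nor the central serum chemistry list has them. Attachment 1 plans the panel at screening and then on Day 1 of Cycles 2, 3 and 4. The Cycle 1 row has no mark in either combination's schedule. In the durvalumab schedule it is printed in italics, and rows in that font "indicate that there is no planned assessment for the time frame shown on the page".

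Attachment 7 (General Considerations) directs that study drug be held for asymptomatic amylase or lipase of Grade 3 or higher, pending work-up for pancreatitis. Section 5.1.2 gives the background. On monotherapy, amylase rose in 4 and lipase in 9 of 64 patients, mostly Grades 1 and 2, and one patient "developed mild-to-moderate increases in amylase and lipase levels and was ultimately diagnosed with Grade 3 pancreatitis, determined to be dose-limiting".

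**The concern.** The MTD, and through it the Part B dose, rests on the Cycle 1 DLT count. One laboratory criterion in that count has no planned measurement in the period over which it is counted. Amendment (b) revised the DLT criteria for AST, CK, amylase and lipase together. AST and CK are then drawn throughout Cycle 1, while amylase and lipase are not drawn at all.

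The same gap affects safety. On weekly dosing, all four Cycle 1 doses of LY3022855 are due before the first planned post-dose amylase or lipase value, so the Attachment 7 hold rule has no planned Cycle 1 input. The error also has one direction: an unseen event can only lower the count and make a dose look more tolerable.

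**Working it through.** **1. Which enzyme findings could be DLTs (section 7.2.2.1)**

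| Finding in Cycle 1 | Status |
|---|---|
| Grade 3, isolated, asymptomatic, no organ damage | Excluded |
| Grade 3 with organ damage | Not excluded. DLT if a non-irAE; if an irAE, DLT only if it fails the 3-day or 14-day downgrade test |
| Grade 4 | Not excluded. Listed as a DLT whether classed as irAE or non-irAE |

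The opening sentence adds that the event does not improve to Grade 2 or below despite management, unless stated otherwise. Applying that test, or the downgrade tests, needs serial values.

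**2. What is planned (Attachments 1 and 2, both combinations)**

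| Analyte | Cycle 1 days | Next |
|---|---|---|
| AST, ALT, bilirubin, CK (serum chemistry) | 1, 8, 15, 22 (central also Day 2) | Cycle 2 Day 1 |
| Amylase, lipase (pancreas panel) | none | Cycle 2 Day 1 |

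**3. Calendar.** Cycle 2 Day 1 is nominally study Day 28 + 1 = 29. With the 3-day window either side it falls on Days 26 to 32. Only a draw on Days 26 to 28 lies inside the 28-day cycle. Day 29 is exactly 28 days after Day 1, so even the nominal date is open to two readings of the evaluability sentence. No text says how an elevation first seen there is classed.

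**4. Possible size, by illustration.** The point rests on no figure in the plan. As a check on the design as read, the Part A total reproduces: durvalumab 4×6 + 2×6 = 36, tremelimumab 4×6 + 3×6 = 42, sum 78.

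Any-grade monotherapy rates are lipase 9/64 = 14.1% and amylase 4/64 = 6.3%. No Grade 4 rate and no Cycle 1 rate is given. Let m be the assumed share of patients whose only DLT is an unseen enzyme event.

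Chance that a cohort of 6 contains at least one: 1 − (1 − m)^6.
- m = 2%: 11%
- m = 5%: 26%
- m = 10%: 47%

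Chance that a dose clears (0 of 3, or 1 of 3 followed by 0 of 3), with visible rate p = true rate − m: (1 − p)^3 + 3p(1 − p)^5.

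| True DLT rate | m | p | Chance of clearing |
|---|---|---|---|
| 30% | 0 | 0.30 | 0.343 + 0.151 = 49% |
| 30% | 5% | 0.25 | 0.422 + 0.178 = 60% |
| 30% | 10% | 0.20 | 0.512 + 0.197 = 71% |
| 33% | 0 | 0.33 | 43.4% |
| 33% | 1/64 | 0.314 | 46.5% |
| 33% | 5% | 0.28 | 53.6% |

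At a true rate of 33% the shift is 3.1 points for m = 1/64 and 10.1 points for m = 5%.

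How plausible is m? Against the any-grade lipase rate, m = 5% needs 5/14.1 = 36% of those elevations to be asymptomatic, DLT-qualifying and in Cycle 1; m = 10% needs 71%. Since most were Grades 1 and 2, these values look high.

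**The case against.** A reader might infer that the trial cannot detect asymptomatic pancreatic DLTs. The documents do not support that. Attachment 1 allows assessments as clinically required. The Cycle 2 Day 1 sample is taken before infusion, so it reflects Cycle 1 exposure and can show an elevation that has persisted. The commonest candidate, isolated asymptomatic Grade 3, is excluded from the DLT definition. Under the opening sentence of 7.2.2.1, an elevation that resolves may arguably not be a DLT at all. All of this stands and narrows the gap. It does not close it: an asymptomatic patient gives little reason to order a test, and the itemized Grade 4 entries carry no resolution condition.

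A reader might also take the monotherapy pancreatitis case (one of 5 patients treated at 1.25 mg/kg QW in section 5.4.1) as a measure of the rate missed. It is not. That case was diagnosed Grade 3 pancreatitis with mild-to-moderate enzyme rises, so it shows a relevant organ toxicity but not a silent Grade 4 value. Nor does the point extend to total LDH, which section 7.2.4.1.1 names for monitoring but the DLT definition does not mention.

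There are other safeguards. Escalation can stop at any time on available safety data, DLETs count toward the 33% review trigger in Part B, and the RP2D may be revised on Part B data. These limit the consequences but do not supply the missing Cycle 1 values. Finally, every laboratory test at Cycle 2 Day 1 shares the boundary problem, but AST and CK have earlier Cycle 1 values to fall back on.

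**Conclusion.** The point holds in a limited form. Following the schedule exactly leaves one stated DLT criterion and one hold rule with no planned Cycle 1 data, in both combinations. The exposed events are asymptomatic Grade 4 elevations, and Grade 3 elevations with silent organ damage, that arise and resolve within Cycle 1. Elevations that persist can be seen on Cycle 2 Day 1, but whether they are then DLTs or DLETs is undefined.

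It would be too strong to say that DLT counts will be too low. Any error runs in that direction, but its size is unknown. The clearance figures depend on an assumed m, and on those patients having no other DLT. The shift is a few points at 1/64 and about ten at 5%. This is worth an amendment because the gap is real and cheap to close; a material bias in the MTD has not been shown.

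**What to change.** Reconcile section 7.2.2.1, Attachment 7 and Attachment 1.

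- In Attachment 1, for both combinations, add the Pancreas function panel to Part A Cycle 1 visits that already have a central chemistry draw. The post-dose ones are Days 2, 8, 15 and 22; the sponsor should choose among them and give the reason.
- In section 7.2.2.1, state how an elevation first seen in the pre-infusion Cycle 2 Day 1 sample is attributed, DLT or DLET, whatever the calendar day of the draw.
- Say whether these results must be reviewed before the next dose. Attachment 1 now requires that only for local chemistry, while the pancreas panel is central.

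The cost is two more analytes on visits that already send blood to the central laboratory, a schedule amendment, and a few more laboratory findings to adjudicate. No visit or procedure is added, and the sample size does not change.

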5.1.2. Summary of the Rationale for Amendment (b)

Amendment (b) was created to incorporate the following changes:

- Modification of enrollment criteria in terms of prior treatment to reflect the changing landscape of cancer therapies.

- Dosing modification and toxicity management guidelines for immune-mediated, infusion-related, and non-immune-mediated reactions included under Table JSCC.5, Table JSCC.6, and Table JSCC.7 have been moved to [Attachment 7](#) with no content changes.
- Cohort #3 (LY3022855 in combination with durvalumab in patients with melanoma), Cohort #4 (LY3022855 in combination with tremelimumab in patients with mesothelioma), and Cohort #5 (LY3022855 in combination with tremelimumab in patients with melanoma) from Part B of the study was removed. These changes were made for strategic reasons, and not for any identified safety concerns. The dose escalation of LY3022855 in combination with tremelimumab in Part A of the study will be completed, should this combination be developed in the future.
- Adverse events of special interest (AESIs) observed with durvalumab or tremelimumab were modified in Section [7.2.4.1.1](#) and [Attachment 8](#) for consistency with durvalumab investigator's brochure (IB) and tremelimumab IB.
- Dose-limiting toxicity (DLT) criteria (creatinine kinase[CK] elevation $>8\times$ upper limit of normal [ULN]) for CK was added for consistency with the toxicity management and dose modification guidelines listed in Attachment 7 of I5F-MC-JSCC (JSCC) protocol, non-immune-mediated reactions. These guidelines recommend different management for CK elevations that are $>8\times$ ULN compared to CK elevations that are $\leq 8\times$ ULN.
- Modification of DLT criteria to allow flexibility to continue dosing with Grade ≥ 2 elevations of aspartate aminotransferase (AST), CK, amylase, and lipase in certain situations as described in Section [7.2.2.1](#) based on the following rationale:

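### Section 7.2.2.1 lists asymptomatic isolated AST >8–20 × ULN and asymptomatic, myoglobin-negative CK >8–10 × ULN both as DLTs and as DLT exclusions; both exclusions should be capped at 8 × ULN

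*Protocol*

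**What the plan says.** Protocol Section 7.2.2.1 introduces its DLT list with "The following are considered DLTs, unless noted otherwise". Under nonhematologic toxicity the list includes "any liver transaminase elevation" above 8 × ULN, CK above 8 × ULN, and "any Grade 3 or 4 non-irAE except as noted for transaminases, bilirubin, lipase, or amylase below". CK is not among that last bullet's exceptions.

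A second list opens with "The DLT definition excludes the following conditions". Two of its items matter here:

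- "Asymptomatic Grade 3 AST induction that is accompanied by Grade" ≤1 ALT and total bilirubin, both unchanged from baseline;
- asymptomatic Grade 3 CK, stated as 5–10 × ULN, "that is not associated with elevated serum or urinary myoglobins and no evidence of rhabdomyolysis or myositis".

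Neither item stops at 8 × ULN. The opening definition also limits DLTs to events that fail to improve to Grade ≤2 with treatment, save where an item provides otherwise.

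Attachment 7 puts Grade 3 AST at >5 to 20 × ULN. Its allowance for isolated asymptomatic Grade 3 AST ends at 8 × ULN, and above that the regimen is discontinued. For asymptomatic Grade 3 CK above 8 × ULN without organ damage, LY3022855 is held and the partner drug may resume after discussion with the sponsor. LY3022855 restarts at ≤8 × ULN, and both drugs stop for good only if CK stays above 8 × ULN.

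Section 5.1.2 explains that the CK >8 × ULN criterion "for CK was added for consistency with the toxicity management and dose modification guidelines listed in Attachment 7". The SAP does not define a DLT; Section 6.8.2 only summarizes them.

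**The concern.** The same laboratory result can be classified two ways, and no sentence says expressly which way holds for the >8 × ULN lines. The literal reading favors the exclusions; the stated reason for adding the CK line points the other way.

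DLT counts drive escalation and the MTD (Section 7.2.2.2, Table JSCC.3), so the choice can decide whether a dose level is passed. The Part B safety review in Section 7.2.3 is triggered by DLTs or DLETs in 33% or more of a cohort. Because DLETs are defined as later events that meet the DLT criteria, that trigger carries the same conflict.

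The enzymes concerned are the ones LY3022855 is known to raise: Section 5.1.2 reports AST rises in 19 and CK rises in 17 of 64 monotherapy patients, mostly Grade 1–2.

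**Working it through.** **Overlap of the two lists** (asymptomatic, isolated or myoglobin-negative events)

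| | DLT list | Exclusion | Both | Attachment 7 in the overlap |
|---|---|---|---|---|
| AST | >8 × ULN | Grade 3, >5–20 × ULN | >8–20 × ULN | Discontinue regimen |
| CK | >8 × ULN | Grade 3, 5–10 × ULN | >8–10 × ULN | Hold LY3022855; stop both only if CK stays >8 × ULN |

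**What the CK line does on the literal reading.** For non-immune events, Grade 4 CK (>10 × ULN) and symptomatic Grade 3 CK are already DLTs through the Grade 3 or 4 non-irAE bullet. The line's distinct use is therefore mainly the asymptomatic band of >8–10 × ULN, which is what the exclusion removes.

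**The 3+3 rule.** The plan states no figure for this point. Its Part A sizes do confirm the cohort structure: minimum 4 × 3 = 12 per combination; maximum 4 × 6 + 2 × 6 = 36 with durvalumab and 4 × 6 + 3 × 6 = 42 with tremelimumab; 36 + 42 = 78.

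**Effect on a decision.** In 6 patients with one other DLT and one band event, the count is 1/6 (escalate) if the band event is excluded and 2/6 (stop) if it counts. In Part B, with the minimum of 6 patients, 2/6 = 33.3% reaches the review trigger and 1/6 = 16.7% does not.

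**Effect on the chance of clearing a level.** Clearing means 0/3, or 1/3 followed by 0/3:

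P(clear) = (1 − p)³ + 3p(1 − p)⁵

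Let d be the rate of other DLTs and b the rate of band events in Cycle 1, taken as independent.

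- Band event counts: p = 1 − (1 − d)(1 − b)
- Does not count, patient kept as a non-DLT: p = d
- Does not count, patient leaves in Cycle 1 and is replaced as nonevaluable (Section 7.6.1): p = d / [1 − (1 − d)b]

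Both rates are assumptions. The nearest documented figure is 1 of 64 monotherapy patients (1.6%) discontinued for drug-related CK and AST rises. It is not a band rate, and it arose at 2.5 mg/kg QW (2.5 × 75 = 187.5 mg at 75 kg), above this trial's 100 mg maximum.

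With d = 10%, the kept value is 0.729 + 0.3 × 0.590 = 0.906.

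| b | p if counted | Counted | Kept | Replaced | Excess, kept | Excess, replaced |
|---|---|---|---|---|---|---|
| 1/64 | 0.114 | 0.882 | 0.906 | 0.904 | 2.4 points | 2.2 points |
| 2% | 0.118 | 0.875 | 0.906 | 0.903 | 3.1 points | 2.8 points |
| 5% | 0.145 | 0.824 | 0.906 | 0.898 | 8.2 points | 7.5 points |

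The kept excess for the same three band rates is 1.7, 2.2 and 6.3 points at d = 5%, and 2.7, 3.5 and 8.7 points at d = 20%.

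**The case against.** **The text has a precedence rule.** A general list followed by exclusions is ordinary drafting, and the exclusions prevail. That is the right literal reading, but it does not explain why a CK >8 × ULN line was added for consistency with Attachment 7 and then largely removed.

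**Ending treatment and being a DLT are different things.** A reader might infer that any event that stops treatment must be a DLT. The protocol does not support that. A first Grade 3 infusion reaction resolving within 6 hours can be excluded from DLTs, yet any Grade ≥3 reaction ends treatment (Section 7.2.1.1); conversely, a patient with a DLT may continue by agreement. Attachment 7 manages dosing and does not define DLTs. This objection stands against the broad inference. What remains for AST is narrower: Attachment 7 draws its isolated-AST allowance at 8 × ULN, the same line as the DLT list, and the exclusion passes over it. Amendment (b)'s aim of letting dosing continue does not reach an event after which dosing is discontinued.

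**CK is compatible with non-DLT status.** The exclusion visibly runs to 10 × ULN, and Attachment 7 holds before it stops. This stands: a reader might infer a direct contradiction for CK as well, but the documents show only a mismatch of thresholds.

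**The practical effect may be small.** Section 5.4.1 says enzyme rises fell below Grade 2 once LY3022855 stopped, so under the improvement clause many band events might not be DLTs on either reading. The 2% and 5% rates have no documentary basis. Both points stand and make the figures upper bounds.

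**Central review limits inconsistency.** Escalation needs documented agreement of the investigator, the sponsor's team and the collaborator (Section 7.2.2). That is a real safeguard, but it leaves the counting rule in Table JSCC.3 unchanged.

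**Conclusion.** The double classification is in the text and should be corrected. For AST it leaves out of the DLT count an event above the 8 × ULN limit that Attachment 7 sets for isolated rises. For CK it largely cancels a line the sponsor added on purpose.

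Under assumed band rates of 1.6–5%, 10% other DLTs and independence, the chance of clearing a dose level is at most about 2 to 8 points too high. It is less if events that improve to Grade ≤2 do not count.

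A reader might infer from the 17 and 19 of 64 patients that band events are common. Those counts are mostly Grade 1–2, and the documents give no rate for either band. Nor do the documents show that any Part A event fell in a band or that the MTD is wrong.

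**What to change.** By amendment to Section 7.2.2.1:

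- cap both exclusions, AST and CK, at ≤8 × ULN;
- add CK to the exceptions in the Grade 3 or 4 non-irAE bullet;
- state whether the >8 × ULN lines apply even if the value later improves to Grade ≤2.

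Re-read any Part A events in the two bands before the MTD is confirmed.

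The evaluability rules need no change for this purpose. Once a >8 × ULN event counts as a DLT, a patient who stops in Cycle 1 because of it is already evaluable under Protocol Section 7.6.1 and SAP Sections 5.1 and 6.2. Do not add a rule that keeps patients who miss Cycle 1 doses for events ≤8 × ULN as evaluable non-DLTs: it would count under-dosed patients as having tolerated the dose.

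The cost is a few words and a review of existing laboratory data, with no new procedures. Slightly more DLTs may be counted, which could expand a cohort to 6 patients or stop escalation one level earlier.
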